#### 2.7.1.3 Daytime and nighttime asthma symptoms

The baseline of asthma daytime symptom diary (ADSD) and asthma nighttime symptom diary (ANSD) will be defined as the average of the respective scores during the run-in period.

The mean daily scores of ADSD and ANSD will be summarized by weekly intervals.

#### 2.7.1.4 AQLQ+12

AQLQ (Asthma Quality of Life Questionnaire) is a 32-item disease specific questionnaire designed to measure functional impairments that are most important to patients with asthma, with 7-point scale (1-totally limited/problems all the time, 7-not at all limited/no problems). It consists of 4 domains: symptoms, emotions, exposure to environmental stimuli and activity limitation. Mean score will be calculated for the four domains, as well as the overall quality-of-life score defined as the mean score of all 32 items.

The average change from baseline in AQLQ+12 (overall and by domain) at Week 8 and Week 12 will be analyzed using the same MMRM model as specified for the primary efficacy variable with baseline AQLQ as covariate. The estimated adjusted treatment difference at each visit as well as the average between Week 8 and Week 12 will be reported along with the associated 95% confidence interval.

The proportion of patients who achieve an improvement of at least 0.5 in the change from baseline in AQLQ (i.e. increase of AQLQ score of at least 0.5 from baseline) at post-baseline visits will be analyzed using the same repeated measurements logistic regression model for the ACQ-5 analysis except that baseline AQLQ will be used instead of the baseline ACQ-5. The estimated adjusted odds ratios at each visit will be displayed along with the associated 95% confidence intervals.

#### 2.7.1.5 Total daily use of SABA

Total daily use of short-acting  $\beta$ -agonist (SABA) (the number of puffs taken in the previous 24 hours) by the patient will be analyzed using ePEF/eDiary data. The baseline of SABA use will be defined as the average of total daily SABA use during the run-in period.

The mean daily use of SABA will be summarized by weekly intervals.

#### 2.7.1.6 Peak Expiratory Flow Rate (PEF)

E-diary data recorded during the run-in period will be used to calculate the baseline value.

Mean morning/evening PEF will be summarized by treatment and by weekly intervals. .

#### 2.8 Safety analyses

Safety summaries include only data from the on-treatment period with the exception of baseline data which will also be summarized where appropriate (e.g. change from baseline summaries).

In addition, a separate summary for death including on treatment and post treatment deaths will be provided.

All safety analysis will be performed on the Safety Set.

#### 2.8.1 Adverse events (AEs)

An adverse event (AE) is any untoward medical occurrence (e.g. any unfavorable and unintended sign [including abnormal laboratory findings], symptom or disease) in a subject or clinical investigation subject after providing written informed consent for participation in the study. All treatment emergent adverse events (AEs) including asthma exacerbations will be summarized.

Summaries will be provided by MedDRA primary system organ class, preferred term, and treatment group showing the number and percentage of patients with events for the on-treatment and off-treatment periods, respectively, as defined below:

on-treatment period (Safety Set): AE started or worsened in [Day 1, last treatment day]; off-treatment period (Only include patients in the Safety Set who had at least one day in the off-treatment period): AE started or worsened in [last treatment day + 1 day, last treatment day + 30 days].

The rationale to summarise AE by on- and off- treatment periods is that for patients who complete the 12-week treatment and enter the extension study immediately, they will not have any AEs reported in the off-treatment period. For other patients, they would potentially have data from both the on- and off-treatment period (either in the follow up epoch or discontinue the treatment but remained on study). Therefore, to avoid the mixture of these patients, we split AEs into on- and off-treatment summaries.

Note that in the off-treatment AE summary, only patients who had at least one day in the offtreatment period will be included. Since there could be imbalance in such patient population across different treatment arms, there is no causal interpretation for the comparison. To aid the

For business use only

interpretation, the total sum of off-treatment days will also be reported in each arm in the off-treatment AE summary tables.

Summaries will be presented in the following ways:

- by treatment and preferred term (PT).
- by treatment, primary system organ class (SOC) and PT.
- by treatment, SOC, PT and maximum severity.

Separate summaries by SOC and PT will be provided for :

• serious adverse events (SAEs)

Further SAEs will be summarized by PT separately for on-treatmnet and off-treatment periods.

Unless otherwise specified, SOCs will be sorted alphabetically and, within each SOC, the PTs will be sorted in descending order of frequency in the highest CSJ117 dose. A subject with multiple adverse events within a SOC or PT is only counted once towards the total of the SOC or PT.

Listings will be provided for all AEs, SAEs and fatal AEs.

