CSJ117 is a potent neutralizing antibody fragment (fragment antigen-binding, Fab) directed against human TSLP. CSJ117 is formulated as a PulmoSolTM engineered powder in hard capsules for delivery to the lungs *via* dry powder inhaler (DPI). Compared to a full length antibody, CSJ117 does not have the Fc region and only contains the antigen binding region. Consequently the molecular weight of CSJ117, 46.6 kDa, is smaller than the molecular weight of a full length antibody, ~150 kDa. Once absorbed into the systemic circulation, the Fab molecule is expected to be cleared faster than a full length antibody, due to the smaller size of the Fab and the lack of neonatal Fc receptor binding. In the absence of target-mediated disposition, the systemic terminal elimination half-life (T¹/₂) in humans for a Fab typically ranges from 14 to 25 hours (Schaumann et al 1986, Czock et al 2012, Morris et al 2012) versus approximately 23 days for a full length IgG monoclonal antibody (mAb) (Lobo et al 2004).

The use of an anti-TSLP Fab molecule with a DPI formulation is expected to result in improved lung distribution and tissue penetration as compared to a full length systemically delivered antibody, due to the smaller size of the Fab and targeted delivery to the lung. CSJ117, as an inhaled Fab targeting TSLP, offers the potential to be an efficacious therapy for moderate to severe asthma with a favorable safety and tolerability profile.

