6.7.2 Instruction for prescribing and taking study treatment

The instructions for the investigational drug (CSJ117/placebo) are as follows:

- CSJ117 PulmoSol powder / placebo is provided in a hard capsule to be inhaled via the Concept1 device
- CSJ117/placebo should be taken by patient once a day at approximately the same time each morning together with his/her maintenance ICS/LABA treatment (Fluticasone propionate/salmeterol)

Instructions for fluticasone propionate/salmeterol and rescue medication should be according to the respective product label.

On the run-in visit a medication kit with placebo capsules and a Concept1 inhalation device will be provided for demonstration and training purposes. On this visit, all patients will be fully trained in the correct use of the Concept1 devices used to administer study medication. Patients who are unable to use the device correctly at the end of run-in visit (Day 1) will not be eligible to enter the treatment epoch.

On study visit days, patients should be reminded **not** to take the investigational drug (CSJ117/placebo) prior to the visit to ensure compliance with the pre-dose PK sampling procedure.

On the day prior to and on days of visits, with the study drug administration, patients should be reminded not to take fluticasone/salmeterol in order to ensure compliance with the spirometry pre-dose measurements.

The morning dose of fluticasone/salmeterol on the visit days should be taken after spirometry assessments and the pre-dose PK sampling have been both completed. The evening dose of fluticasone/salmeterol on visit days should be taken as usual.

7 Informed consent procedures

Eligible subjects may only be included in the study after providing (witnessed, where required by law or regulation), IRB/IEC-approved informed consent.

If applicable, in cases where the subject's representative(s) gives consent (if allowed according to local requirements), the subject must be informed about the study to the extent possible given

his/her understanding. If the subject is capable of doing so, he/she must indicate agreement by personally signing and dating the written informed consent document.

Informed consent must be obtained before conducting any study-specific procedures (e.g. all of the procedures described in the protocol). The process of obtaining informed consent must be documented in the subject source documents.

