12.5.2 Safety endpoints

Safety summaries include only data from the on-treatment period with the exception of baseline data which will also be summarized where appropriate (e.g. change from baseline summaries). In addition, a separate summary for death including on treatment and post treatment deaths will be provided.

Adverse events

For patients not entering the safety extension study directly after the treatment period or not participating in the safety extension study, the on-treatment period for adverse events (AEs) lasts from the time of first administration of double-blind study treatment to 30 days after the time of the last administration of randomized study treatment. For patients entering the safety extension study directly after the treatment period, the on-treatment period lasts from the time of first administration of double-blind study treatment to the time of the last actual administration of randomized study treatment. Summary tables for AEs will summarize only on-treatment events (also known as treatment-emergent AEs).

All information obtained on adverse events will be summarized by treatment group.

The number (and percentage) of subjects with treatment emergent adverse events will be summarized separately for the treatment period and the follow-up period (30 days after the last time of the last administration of randomized study treatment) in the following ways:

- by treatment, primary system organ class and preferred term.
- by treatment, primary system organ class, preferred term and maximum severity.
- by treatment, Standardized MedDRA Query (SMQ) and preferred term.

Separate summaries will be provided for study medication related adverse events, death, serious adverse events, other significant adverse events leading to discontinuation separately for the treatment period and the follow-up period (30 days after the last time of the last actual administration of randomized study treatment).

A subject with multiple adverse events within a primary system organ class or preferred term is only counted once towards the total of the primary system organ class or preferred term.

Vital signs

Summary statistics will be provided by treatment and visit/time for each vital signs variable. Notable values (to be defined in the SAP) and change from baseline will also be summarized. The baseline value is the last value prior to first dose of double-blind treatment.

12-lead ECG

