#### 2.1.1.3 Post-baseline definition

All data collected after the start of double-blind treatment are defined as post-baseline. For patients who are not treated, the post-baseline is any assessments after randomization.

When change from baseline is of interest the following formula will be used for each scheduled visit and time-point where baseline and post-baseline values are both available:

Change from baseline = post-baseline value – baseline value.

If not stated otherwise for efficacy analyses, on-treatment values are defined as values taken post-baseline but no later than 1 day after last dose of double-blind treatment. Off-treatment values are defined as post-baseline values taken more than 1 day after last dose of double-blind treatment.

Details on calculation of post-baseline values are provided in the latter sections.

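### SAP 2.8.1 ends the on-treatment AE period on the calendar day of the last dose, so an overnight reaction that stops treatment is tabulated as off-treatment

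*SAP*

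**What the plan says.** - **AE periods.** SAP 2.8.1 gives two windows in whole days: "on-treatment period (Safety Set): AE started or worsened in [Day 1, last treatment day" and, for off-treatment, "AE started or worsened in [last treatment day + 1 day, last treatment day + 30 days". The by-period SAE tables (2.8.1) and the AESI tables (2.8.1.1) follow the same split. The SAP does not define the last treatment day separately; the date of the last dose is the natural reading.
- **Status of the off-treatment table.** It includes only Safety Set patients with at least one off-treatment day. The SAP adds: "Since there could be imbalance in such patient population across different treatment arms, there is no causal interpretation for the comparison". The stated reason for the split is that patients who go straight into the extension study have no off-treatment AEs, so pooling would mix them with patients who do.
- **Other windows in the SAP.** On-treatment efficacy data are "values taken post-baseline but no later than 1 day after last dose of double-blind treatment" (2.1.1.3). Laboratory, ECG and vital-sign data run to 30 days after the last dose for patients not going directly into the extension (2.8.3, 2.8.4).
- **Protocol 12.5.2.** For patients not going directly into the extension, the on-treatment AE period lasts "to 30 days after the time of the last administration of randomized study treatment". For direct entrants it ends at the last administration. The same section also asks for separate treatment-period and follow-up AE summaries.
- **Dosing.** Protocol 6.7.2: "CSJ117/placebo should be taken by patient once a day at approximately the same time each morning".

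**The concern.** With morning dosing, the night after the last dose spans two calendar days. A patient who doses in the morning, reacts after midnight and does not dose again has an onset date one day after the last treatment day. The event lies within one dosing interval of the drug, yet SAP 2.8.1 files it with events from up to 30 drug-free days.

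The rule does not affect all events alike. If the patient takes another dose after the reaction, the event stays on-treatment. The events that move are those followed by no further dose, which include reactions that made the patient stop. Protocol 4.5 names hypersensitivity and coughing or bronchoconstriction among the major risks, and reactions of that kind could plausibly end dosing. At stake is whether the by-dose on-treatment tables count all of them.

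**Working it through.** No sample size, power or alpha figure bears on this, so there is no planned figure to reproduce. The point rests on date rules.

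**1. Apply the rules.** Take a last dose on study day 20, a complete AE onset date, and a patient not entering the extension directly.

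| AE onset | SAP 2.8.1 | Protocol 12.5.2 | SAP 2.1.1.3 efficacy lag, applied to the same date |
|---|---|---|---|
| Day 20 | on | on | on |
| Day 21 | off | on | on |
| Day 22 | off | on | off |
| Day 50 | off | on | off |
| Day 51 | neither | neither | off |

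The day-21 row is the case at issue. SAP 5.1.2 resolves uncertainty in partial AE dates towards on-treatment, but a complete next-day date is not uncertain, so that rule does not help.

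**2. Share of the 24 hours after the last dose that falls on the next day.** The documents give neither the clock hour of dosing nor the onset pattern, so both are assumptions. For a dose at hour h, midnight comes 24 − h hours later.

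- Uniform onset: s = h/24. At 06:00, 6/24 = 25%; at 08:00, 8/24 = 33%; at 10:00, 10/24 = 42%.
- Onset clustered after inhalation: exponential with mean m (before truncation), truncated at 24 hours, 08:00 dose. Then s = (e^(−16/m) − e^(−24/m)) / (1 − e^(−24/m)).
  - m = 2 h: (0.000335 − 0.000006)/0.999994 = 0.03%
  - m = 4 h: (0.0183 − 0.0025)/0.9975 = 1.6%
  - m = 8 h: (0.1353 − 0.0498)/0.9502 = 9.0%

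**3. Patients moved.** SAP 1.1 gives 335 enrolled. At 2:1:1:1:2:2, a double-size arm has about 335 × 2/9 = 74.4 patients and a single-size arm 335/9 = 37.2. Let p be the proportion who stop because of a reaction starting within 24 hours of their last dose. The documents give no p; 5% (range 2% to 10%) is assumed. Patients moved = 74.4 × p × s.

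| p (assumed) | Such patients per double-size arm | Moved, s = 33% | Moved, s = 9% | Moved, s = 0.03% |
|---|---|---|---|---|
| 2% | 1.5 | 0.5 | 0.1 | < 0.01 |
| 5% | 3.7 | 1.2 | 0.3 | < 0.01 |
| 10% | 7.4 | 2.5 | 0.7 | < 0.01 |

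In a single-size arm one moved patient is 1/37.2 = 2.7 percentage points.

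**4. Effect on a dose contrast.** If s is the same in every arm, the on-treatment table shows (1 − s)p. The dose-minus-placebo difference in these reactions is multiplied by 1 − s: 0.67 for uniform onset at 08:00, 0.91 for m = 8 h. The ratio between arms is unchanged. If p is equal across arms, the difference stays at zero.

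**5. Residual drug.** Protocol 1.1 says the serum half-life "in humans for a Fab typically ranges from 14 to 25 hours". At 24 hours, 2^(−24/14) = 30% to 2^(−24/25) = 51% would remain. At 48 hours, 2^(−48/14) = 9% to 2^(−48/25) = 26% would remain.

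**The case against.** The case for leaving the rule alone is substantial, and much of it stands.

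- **The events are not lost.** A reader might infer that these reactions disappear. They do not. They remain by arm in the off-treatment tables, with total off-treatment days reported, and in the AE, SAE and AESI listings. Deaths are summarised across both periods (SAP 2.8), and reasons for stopping treatment are tabulated by arm (SAP 2.4.1).
- **The Protocol also splits the periods.** A reader might infer that the SAP simply overrides a 30-day window. Protocol 12.5.2 does call those 30 days on-treatment for patients not going directly into the extension, but it also wants treatment-period and follow-up events shown separately. The contrast is partly one of labels.
- **The on-treatment table is not declared the only fair comparison.** The SAP disclaims causal interpretation for the off-treatment table ("there is no causal interpretation for the comparison"). It makes no matching affirmation for the on-treatment one.
- **A large share or a dose-dependent loss is not shown.** The figures of 25% to 42% need uniform onset. Protocol 4.5 ties cough and bronchospasm to local irritation from inhalation, which suggests earlier onset and a far smaller share. It also reports no discontinuations due to AEs in the three completed studies, including 12 weeks at 4 mg.
- **Half-life does not select one day.** The range is for Fab molecules in general, concerns serum rather than the airway, and leaves some drug at 48 hours too. The efficacy lag has its own reason: pre-dose FEV1 can be measured the morning after the last dose.

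What does not stand is the view that the split requires zero lag. SAP 2.8.1 justifies it by patients who complete 12 weeks and move straight into the extension. Patients who stop early because of a reaction are not among them.

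**Conclusion.** The misfiling is real and follows directly from the text: a fully dated reaction that starts after midnight, within 24 hours of the last morning dose, and ends treatment is counted as off-treatment. It is a relocation into tables with a selected denominator, not a loss of data. Its size is unknown. Under the assumptions shown it ranges from effectively no patients to about 2.5 in a double-size arm at 08:00 dosing. It shrinks a between-dose difference in absolute terms only if such reactions differ by dose, and the documents offer no evidence on that. This is a cheap improvement to the AE tables rather than a threat to the trial's safety conclusions.

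**What to change.** In SAP 2.8.1, define the on-treatment AE period as [Day 1, last treatment day + 1 day], in line with SAP 2.1.1.3. Cap it at the last visit of this study for patients who enter the extension directly. Start the off-treatment period at last treatment day + 2 days, leaving its end at + 30 days. Carry the same periods into the by-period SAE tables, the AESI tables (2.8.1.1), and the off-treatment denominators and day totals.

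The cost is one line of wording and one derivation flag. Patients who do not enter the extension directly gain up to one day in a window of about 85 days (Day 1 to the Week 12 visit on Day 85). That may add an occasional unrelated event, and it brings back a very small part of the mixture that the split was meant to avoid.

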#### 2.8.1.1 Adverse events of special interest / grouping of AEs

The number and percentage of patients who reported treatment-emergent adverse events of special interest (AESI) will be summarized by risk name, PT and treatment group separately on-treatment and off-treatment periods.

Risk names will be sorted alphabetically and, within each risk name, the PTs will be sorted in descending order of frequency in the highest CSJ117 dose. If a patient reported more than one adverse event with the same PT, the AE will be counted only once. If a patient reported more than one AE within the same risk, the patient will be counted only once at that risk.

The Compound Case Retrieval Strategy (CRS) will be used to determine the MedDRA search criteria to be used to identify AESI. The most recent list of adverse events of special interest at the time of database lock will be used.

A listing for all AESI will be provided.

#### 2.8.1.2 AE reporting for CT.gov and EudraCT

For the legal requirements of clinicaltrials.gov and EudraCT, two required tables on treatment emergent adverse events which are not serious adverse events with an incidence greater than 2% and on treatment emergent serious adverse events and SAE suspected to be related to study treatment will be provided by system organ class and preferred term on the safety set population.

If for a same patient, several consecutive AEs (irrespective of study treatment causality, seriousness and severity) occurred with the same SOC and PT:

• a single occurrence will be counted if there is ≤ 1 day gap between the end date of the preceding AE and the start date of the consecutive AE

Novartis SAP

• more than one occurrence will be counted if there is > 1 day gap between the end date of the preceding AE and the start date of the consecutive AE

For occurrence, the presence of at least one SAE / SAE suspected to be related to study treatment / non SAE has to be checked in a block e.g., among AE's in  $a \le 1$  day gap block, if at least one SAE is occurring, then one occurrence is calculated for that SAE.

The number of deaths resulting from SAEs suspected to be related to study treatment and SAEs irrespective of study treatment relationship will be provided by SOC and PT.

#### 2.8.2 Deaths

Fatal AEs will be summarized and listed as specified in Section 2.8.1.

#### 2.8.3 Laboratory data

Summaries of laboratory data will include on-treatment measurements, which are defined as measurements taken post-baseline but no later than 30 days after last dose of double-blind treatment for patients not entering the safety extension study (as described in Section 1.1) directly after the treatment period or not participating in the safety extension study. For patients entering the safety extension study directly after the treatment period, the on-treatment period lasts from the date of first administration of double-blind treatment to the date of the last actual administration of double-blind treatment.

For selected laboratory tests, the number and percentage of patients with newly occurring or worsening laboratory abnormalities meeting the clinically notable criteria at any time on-treatment, considering all on-treatment data from scheduled, unscheduled and premature discontinuation visits, will be summarized by laboratory parameter. Notable criteria are defined in Section 5.3.

Furthermore, the number and percentage of patients with newly occurring or worsening abnormalities in liver function tests (LFT) will be summarized by treatment and at any time on-treatment considering all on-treatment data from scheduled, unscheduled and premature discontinuation visit. LFT criteria are defined in Section 5.3.

The baseline value is the last value prior to first dose of double-blind treatment.

Laboratory data of patients with notable values will be listed.

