#### 2.8.4 Other safety data

#### 2.8.4.1 ECG and cardiac imaging data

Summaries of ECG data will include on-treatment measurements, which are defined as measurements taken post-baseline but no later than 30 days after last dose of double-blind treatment for patients not entering the safety extension study (as described in Section 1.1) directly after the treatment period or not participating in the safety extension study. For patients entering the safety extension study directly after the treatment period, the on-treatment period lasts from the date of first administration of double-blind treatment to the date of the last actual administration of double-blind treatment. Triplicate ECGs and single ECGs will be performed at different visits specified in the assessment schedule table in the protocol. For the analysis of

For business use only

continuous ECG parameter involving triplicate ECGs, the mean value of the 3 ECG measurements will be used; for ECG interpretation, all findings of the 3 ECGs will be considered.

The number and percentage of patients with newly occurring or worsening notable Fridericia's QTc values will be summarized at any time on-treatment, considering all on-treatment data from scheduled, unscheduled and premature discontinuation visits. For derivation of notable values for the triplicate ECGs, the mean of the three ECGs will be used. Notable criteria are defined in Section 5.4.

The number and percentage of patients with ECG abnormalities will be summarized by evaluation type, abnormality finding, visit and time point. The baseline value is the last value prior to first dose of double-blind treatment.

ECG data of patients with notable Fridericia's QTc values will be listed.

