#### 2.8.4.2 Vital signs

Summaries of vital signs data will include on-treatment measurements, which are defined as measurements taken post-baseline but no later than 30 days after last dose of double-blind treatment for patients not entering the safety extension study (as described in Section 1.1) directly after the treatment period or not participating in the safety extension study. For patients entering the safety extension study directly after the treatment period, the on-treatment period lasts from the date of first administration of double-blind treatment to the date of the last actual administration of double-blind treatment.

The number and percentage of patients with newly occurring or worsening notable vital sign values will be summarized at any time on-treatment, considering all on-treatment data from scheduled, unscheduled and premature discontinuation visits. Notable criteria are defined in Section 5.4.

The baseline value is the last value prior to first dose of double-blind treatment.

Vital sign data of patients with notable values will be listed.

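### For labs, ECG and vital signs the on-treatment window depends on extension entry, so off-drug values enter the notable-value counts for some patients only

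*SAP*

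**What the plan says.** Three safety domains share one rule with two tiers. Patients who do not enter the extension directly, or do not take part in it, have their laboratory values counted "no later than 30 days after last dose of double-blind treatment for patients not entering the safety extension study" (SAP 2.8.3). For direct entrants, "the on-treatment period lasts from the date of first administration of double-blind treatment to the date of the last actual administration of double-blind treatment". SAP 2.8.4.1 repeats the rule: "Summaries of ECG data will include on-treatment measurements, which are defined as measurements taken post-baseline but no later than 30 days after last dose", with the same exception for direct entrants. SAP 2.8.4.2 does so for vital signs. The notable-value tables then count a patient with any occurrence in that window, "considering all on-treatment data from scheduled, unscheduled and premature discontinuation visits".

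Other parts of the documents bear on this:

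- SAP 2.8.1 ends the adverse-event on-treatment period at the last treatment day and puts the next 30 days in a separate table. Its reason is "to avoid the mixture of these patients, we split AEs into on- and off-treatment summaries". It also reports total off-treatment days per arm and warns against a causal reading of the off-treatment table.
- SAP 2.1.1.3 uses last dose + 1 day for every patient, for efficacy.
- Protocol 12.5.2 states the two-tier window under adverse events only.
- SAP 1.1 describes follow-up as free of study drug.
- SAP Section 4 removes the by-visit summaries of laboratory variables and vital signs.

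**The concern.** The SAP sees the problem for adverse events and solves it there. It then applies the unsolved form of the window to three other domains and gives no reason. Two things follow. Values from the drug-free period are labelled on-treatment. And the number of chances a patient has to show a notable value depends on whether that patient goes straight into an optional extension, a choice made after randomization. At stake is how the notable laboratory, QTcF and vital-sign counts by arm can be read. With the by-visit laboratory and vital-sign summaries gone, no remaining table for those two domains separates a Week 14 or Week 16 value from a treatment-period value.

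**Working it through.** The documents give no figure for this point, so there is none to reproduce. The check maps the schedule onto the two windows and then puts a size on the difference.

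**Step 1: which follow-up visits fall inside.** Visit days are from Protocol Table 8-1; the last dose is taken as Day 85, because that table shows dosing at Week 12.

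- Window end: 85 + 30 = Day 115.
- Week 14: 99 − 85 = 14 days after the last dose, inside.
- Week 16: 113 − 85 = 28 days, inside.
- Week 20: 141 − 85 = 56 days, outside.

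With the last dose on Day 84 the gaps are 15, 29 and 57 days, and the result is the same. Week 16 is only one or two days inside the limit, so a late visit would drop out.

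**Step 2: scheduled post-baseline assessments counted, for completers who attend on schedule (Table 8-1).**

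| Domain | Direct entrant | Not entering directly |
|---|---|---|
| Blood pressure, pulse | 1 (Week 12) | 2 (adds Week 14) |
| Labs | 4 (Weeks 2, 4, 8, 12) | 5 (adds Week 16) |
| ECG | 4 (Day 1 post-dose, Weeks 4, 8, 12) | 5 (adds Week 16) |

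Vital signs in the abbreviated physical examinations are kept in source documents only and are not counted.

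**Step 3: chance of at least one notable value.** Assume a risk p per assessment, the same on and off drug and in all arms, with independent assessments. The chance over k assessments is 1 − (1 − p)^k. At p = 1%:

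- Labs and ECG: 1 − 0.99^4 = 3.94%; 1 − 0.99^5 = 4.90%; ratio 1.24.
- Vital signs: 1.00%; 1 − 0.99^2 = 1.99%; ratio 1.99.

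Over p = 0.5% to 5% the ratios run from 1.25 to 1.22 and from 2.00 to 1.95. These compare entrants with non-entrants, not arms.

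**Step 4: effect on an arm comparison.** For direct-entry rate e, the arm risk is e × (entrant risk) + (1 − e) × (non-entrant risk). The documents give no entry rates, so these are assumed. With no drug effect and p = 1%:

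- Entry 50% in both arms: ratio 1.00 in all domains.
- 70% active, 50% placebo, labs and ECG: 0.7 × 3.94% + 0.3 × 4.90% = 4.23%, against 4.42%; ratio 0.96.
- 70% active, 50% placebo, vital signs: 0.7 × 1.00% + 0.3 × 1.99% = 1.30%, against 1.50%; ratio 0.87.
- 80% active, 40% placebo: 0.92 for labs and ECG, 0.75 for vital signs.

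**Step 5: absolute size.** With 335 patients randomized 2:1:1:1:2:2, the largest arms have about 335 × 2/9 = 74. At 70% v 50% entry the difference is about 0.2 percentage points at p = 1%, or 74 × 0.002 ≈ 0.15 of a patient. At p = 5% it is 20.59% − 19.77% = 0.8 points for labs and ECG and 7.38% − 6.43% ≈ 1.0 point for vital signs, still under one patient.

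**The case against.** The strongest reply is that no planned table compares entrants with non-entrants. The tables are by arm, and with equal entry the arm ratio stays at 1.00. That stands. A reader might infer from the twofold and 1.2-fold ratios that the dose comparisons are distorted. The documents do not support this, since they give no entry rates by arm. Positive correlation between a patient's assessments would also shrink the ratios.

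A reader might also infer that these counts are now the main safety output. They are not. Adverse-event, serious-event and special-interest tables remain and are already split. ECG abnormalities stay by visit and time point. Patients with notable laboratory, QTcF or vital-sign values are listed, so individual cases can be reviewed.

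The window has a defence: Protocol 12.5.2 uses the same rule for adverse events, and direct entrants have no later visits in this study because Week 12 is their completion visit (Protocol 9.2). A 30-day safety window is reasonable if it is labelled and applied alike. Here it is labelled on-treatment and is not applied alike, so that defence covers only part of the point.

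Finally, a reader might infer that the added values carry no drug effect at all. At the 14 to 25 hour half-life in Protocol 1.1, 14 days is 336/25 = 13 to 336/14 = 24 half-lives. But that is a class figure for systemic Fab elimination, and it does not exclude a delayed effect. What is certain is that no study drug is being taken.

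**Conclusion.** The inconsistency is real and rests on the text alone: two window lengths, chosen by a decision made after randomization, with drug-free follow-up values counted as on-treatment for one group. The scheduled counts (2 v 1, 5 v 4, 5 v 4) follow from Table 8-1 for completers attending on schedule. With equal extension entry and discontinuation across arms, the consequence is added off-drug background events. If these differ by arm, the comparison can be biased; the ratios of about 0.96 and 0.87 are illustrations that depend on the assumed entry rates, no drug effect, independent visits and a 1% risk. They favour active only because entry was assumed higher there. If almost all or almost no patients entered directly, the mixing would largely vanish. Severity is minor to moderate: descriptive safety tables only, with no effect on the primary analysis.

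**What to change.** In SAP 2.8.3, 2.8.4.1 and 2.8.4.2:

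- **One on-treatment window for all patients**, first dose to last dose + 1 day. The extra day keeps Week 12 values when the last dose was the day before. This matters because Protocol 6.1.4 plans 84 days of treatment while Table 8-1 shows dosing on Day 85. Those passages must be reconciled. Under the present rule a direct entrant last dosed on Day 84 loses the Week 12 values, which include the only scheduled on-treatment blood pressure and pulse. State that this cut differs by one day from that in 2.8.1, or align the two.
- **A separate off-treatment table** for later values up to + 30 days, limited to patients with off-treatment assessments and showing the denominator and number of assessments per arm.
- **Combined liver criteria** (SAP 5.3 requires all components within 3 days) evaluated on all data to + 30 days first, then assigned to a period, so that a case straddling the cut is not lost from both tables.

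Reporting direct extension entry by arm would let readers judge the remaining imbalance.

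The cost is SAP wording and a second block in three tables. Discontinuation-visit and repeat-test values taken later than + 1 day move to the off-treatment table; none is discarded.
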